#### Appendix 4 Management of Specific Immune-Related Adverse Events (Continued)

Nephritis or Renal Dysfunction (Elevated Serum Creatinine)		
Consult with Nephrologist		
Monitor for signs and symptoms that may be related to changes in renal function (e.g. routine urinalysis, elevated serum BUN and creatinine, decreased creatinine clearance, electrolyte imbalance, decrease in urine output, proteinuria, etc.)		
Patients should be thoroughly evaluated to rule out any alternative etiology (e.g., disease progression, infections etc.)		
Steroids should be considered in the absence of clear alternative etiology even for low grade events (Grade 2), in order to prevent potential progression to higher grade event		
Grade of AE	Dose Modifications	Toxicity Management
Grade 1 (Serum Creatinine > 1-1.5 × baseline; > ULN to 1.5 × ULN)	
 
No dose modification
 
	
 
Monitor serum creatinine weekly and any accompanying symptom
 
If creatinine returns to baseline, resume its regular monitoring per study protocol.
 
If it worsens, depending on the severity, treat as Grade 2 or Grade 3 or 4
 
Consider symptomatic treatment including hydration, electrolyte replacement, diuretics, etc.
 

Grade 2 (Serum Creatinine > 1.5-3.0 × baseline; > 1.5 ×-3.0 × ULN)	
 
Hold until resolution to ≤ Grade 1 or baseline
 
If toxicity worsens then treat as Grade 3 or Grade 4
 
If toxicity improves to ≤ Grade 1 or baseline resume study drug/study regimen after completion of steroid taper.
 
	
 
Consider symptomatic treatment including hydration, electrolyte replacement, diuretics, etc.
 
Carefully monitor serum creatinine every 2-3 days and as clinically warranted
 
Consult Nephrologist and consider renal biopsy if clinically indicated
 
If event is persistent (> 3-5 days) or worsens, promptly start prednisone 1-2 mg/kg/day PO or IV equivalent
 
If event is not responsive within 3-5 days or worsens despite prednisone at 1-2 mg/kg/day PO or IV equivalent, additional workup should be considered and prompt treatment with IV methylprednisolone at 2-4mg/kg/day started.
 
Once improving gradually taper steroids over ≥ 28 days and consider prophylactic antibiotics, antifungals and anti PCP treatment (refer to current NCCN guidelines for treatment of cancer-related infections [Category 2B recommendation]).
 
When event returns to baseline, resume and routine serum creatinine monitoring per study protocol.
 

Grade 3 or 4 (Grade 3: Serum Creatinine > 3.0 × baseline; > 3.0-6.0 × ULN  Grade 4: Serum Creatinine > 6.0 × ULN)	
 
Permanently discontinue
 
	
 
Carefully monitor serum creatinine on daily basis
 
Consult Nephrologist and consider renal biopsy if clinically indicated
 
Promptly start prednisone 1-2 mg/kg/day PO or IV equivalent
 
If event is not responsive within 3-5 days or worsens despite prednisone at 1-2 mg/kg/day PO or IV equivalent, additional workup should be considered and prompt treatment with IV methylprednisolone 2-4 mg/kg/day started.
 
Once improving, gradually taper steroids over ≥ 28 days and consider prophylactic antibiotics, antifungals and anti PCP treatment (refer to current NCCN guidelines for treatment of cancer-related infections [Category 2B recommendation])
 

#### Appendix 4 Management of Specific Immune-Related Adverse Events (Continued)

Rash (excluding Bullous skin formations)		
Refer to NCICTCAE for definition of severity/grade depending on type of skin rash Monitor for signs and symptoms of dermatitis (rash and pruritus) **IF THERE IS ANY BULLOUS FORMATION, THE STUDY PHYSICIAN SHOULD BE CONTACTED AND STUDY DRUG DISCONTINUED**		
Grade of AE	Dose Modifications	Toxicity Management
Grade 1	
 
No dose modification
 
	
 
Consider symptomatic treatment including oral antipruritics (e.g., diphenhydramine or hydroxyzine) and topical therapy (e.g., urea cream)
 

Grade 2	
 
For persistent (> 1-2 weeks) Grade 2 events, hold until resolution to ≤ Grade 1 or baseline
 
If toxicity worsens then treat as Grade 3
 
If toxicity improves to ≤ Grade 1 or baseline resume study drug/study regimen after completion of steroid taper.
 
	
 
Obtain dermatology consult
 
Consider symptomatic treatment including oral antipruritics (e.g., diphenhydramine or hydroxyzine) and topical therapy (e.g., urea cream)
 
Consider moderate-strength topical steroid
 
If no improvement within 3-5 days or is worsening despite symptomatic treatment and/or use of moderate strength topical steroid, discuss with study physician and promptly start systemic steroids prednisone 1-2 mg/kg/day PO or IV equivalent
 
Consider skin biopsy if persistent for > 1-2 weeks or recurs
 

Grade 3	
 
Hold until resolution to ≤ Grade 1 or baseline
 
If holding does not provide improvement to ≤ Grade 1 or baseline within 30 days, then permanently discontinue
 
	
 
For Grade 3 or 4:
 
Consult dermatology
 
Promptly initiate empiric IV methylprednisolone 1-4 mg/kg/day or equivalent
 
Consider hospitalization
 
Monitor extent of rash [Rule of Nines]
 
Consider skin biopsy (preferably more than 1) as clinically feasible.
 

Grade 4	
 
Permanently discontinue
 
	
 
Once improving, gradually taper steroids over ≥ 28 days and consider prophylactic antibiotics, antifungals and anti PCP treatment (refer to current NCCN guidelines for treatment of cancer-related infections [Category 2B recommendation])
 
Discuss with Study Physician
 

## Appendix 4 Management of Specific Immune-Related Adverse Events (Continued)

Endocrinopathy (e.g., hyperthyroidism, hypothyroidism, hypopituitarism, adrenal insufficiency, etc.)		

 
Depending on the type of endocrinopathy, refer to NCI CTCAE version 4.03 for defining the CTC grade/severity
 
Consult Endocrinologist
 
Monitor patients for signs and symptoms of endocrinopathies. Non-specific symptoms include headache, fatigue, behavior changes, changed mental status, vertigo, abdominal pain, unusual bowel habits, hypotension and weakness.
 
Patients should be thoroughly evaluated to rule out any alternative etiology (e.g., disease progression including brain metastases, infections, etc.)
 
Monitor and evaluate thyroid function tests: TSH, free T3 and free T4 and other relevant endocrine labs depending on suspected endocrinopathy.
 
If a patient experiences an AE that is thought to be possibly of autoimmune nature (e.g., thyroiditis, pancreatitis, hypophysitis, diabetes insipidus), the investigator should send a blood sample for appropriate autoimmune antibody testing
 
		
Grade of AE	Dose Modifications	Toxicity Management
Grade 1	
 
No dose modification
 
	
 
For Grade 1: (including those with asymptomatic TSH elevation)
 
Monitor patient with appropriate endocrine function tests
 
If TSH < 0.5 × LLN, or TSH > 2 × ULN or consistently out of range in 2 subsequent measurements, include FT4 at subsequent cycles as clinically indicated and consider endocrinology consult.
 

Grade 2	
 
For Grade 2 endocrinopathy other than hypothyroidism, hold dose until patient is clinically stable
 
If toxicity worsens then treat as Grade 3 or Grade 4
 
Can resume once event stabilizes and after completion of steroid taper.
 
	
 
For Grade 2: (including those with symptomatic endocrinopathy)
 
Isolated hypothyroidism may be treated with replacement therapy without treatment interruption and without corticosteroids
 
Initiate hormone replacement as needed for management
 
Evaluate endocrine function, and as clinically indicated, consider pituitary scan
 
For patients with abnormal endocrine work up, except for those with isolated hypothyroidism, consider short-term, corticosteroids (e.g., 1-2mg/kg/day methylprednisolone or IV equivalent) and prompt initiation of treatment with relevant hormone replacement (e.g. Levothyroxine, hydrocortisone, or sex hormones).
 
Once improving, gradually taper steroids over ≥ 28 days and consider prophylactic antibiotics, antifungals and anti PCP treatment (refer to current NCCN guidelines for treatment of cancer-related infections [Category 2B recommendation])
 
For patients with normal endocrine work up (lab or MRI scans), repeat labs/MRI as clinically indicated.
 
 
Note: Patients with endocrinopathies who may require prolonged or continued steroid replacement can be retreated on the following conditions: 1) the event stabilizes and is controlled ,2) the patient is clinically stable as per Investigator or treating physician’s clinical judgement, and 3) doses of prednisone are at less than or equal to 10mg/day or equivalent.

Grade 3 or 4 (Depending on the type of endocrinopathy, refer to NCI CTCAE version 4.03 for defining the CTC grade/severity 3 or 4)	
 
For Grade 3 or 4 endocrinopathy other than hypothyroidism, hold dose until endocrinopathy symptom(s) are controlled
 
Can be resume at the next scheduled dose once event stabilizes to grade ≤ 1 and 5-7 days have passed after completion of steroid taper
 
	
 
Consult endocrinologist
 
Isolated hypothyroidism may be treated with replacement therapy without treatment interruption and without corticosteroids
 
Promptly initiate empiric IV methylprednisolone 1-2 mg/kg/day or equivalent
 
Administer hormone replacement therapy as necessary.
 
For adrenal crisis, severe dehydration, hypotension, or shock: immediately initiate intravenous corticosteroids with mineralocorticoid activity
 
Once improving, gradually taper immunosuppressive steroids over ≥ 28 days and consider prophylactic antibiotics, antifungals and anti PCP treatment (refer to current NCCN guidelines for treatment of cancer-related infections [Category 2B recommendation])
 
Discuss with study physician
 

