### 5.1.8 Mocetinostat Adverse Event Management Guidelines

#### 5.1.8.1 Management of Mocetinostat in Response to Immune-Related Adverse Event

Administration of mocetinostat as a single agent or in combination with chemotherapy has not been associated with irAEs. However, the potential exists for mocetinostat to contribute to irAEs associated with durvalumab treatment, which may include immune-mediated enterocolitis, dermatitis, hepatitis, and endocrinopathies. In the event of an irAE, administration of mocetinostat should be interrupted until the event stabilizes to Grade  $\leq 1$  and after completion of any steroid taper (similar to the guidance for resumption of durvalumab treatment as presented in Table 9, and Appendix 4). At the time of resumption of mocetinostat dosing, a dose reduction may be implemented at the discretion of the Investigator.

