**Table 9: Immune-Related Adverse Events, Overall Management**

Durvalumab Treatment Modification	

Drug administration modifications made to manage potential immune-related AEs are based on severity of treatment-emergent toxicities graded per NCI CTCAE v4.03.
 
In addition criteria for permanent discontinuation based on severity (Appendix 4), permanently discontinue for the following conditions:
 
 
• Inability to reduce corticosteroid to a dose of <math>\leq 10</math> mg of prednisone per day (or equivalent) within 12 weeks after last dose of study drug
 
• Recurrence of a previously experienced Grade 3 treatment-related AE following resumption of dosing.
 
	
Grade 1	No dose modification
Grade 2	
Hold study drug dose until Grade 2 resolution to <math>\leq</math> Grade 1
 
 
• If toxicity worsens then treat as Grade 3 or Grade 4
 
 
Study drug/study treatment can be resumed once event stabilizes to Grade <math>\leq 1</math> and after completion of steroid taper.
 
Patients with endocrinopathies who may require prolonged or continued steroid replacement can be retreated on the following conditions:
 
 
1) the event stabilizes and is controlled,
 
2) the patient is clinically stable as per Investigator or treating physician’s clinical judgment, and
 
3) doses of prednisone are at less than or equal to 10mg/day or equivalent.
 

Grade 3	Depending on the individual toxicity, may permanently discontinue. Refer to guidelines below.
Grade 4	
Permanently discontinue
 
Note: For Grade 3 and above asymptomatic amylase or lipase levels hold study drug/regimen and if complete work up shows no evidence of pancreatitis, may continue or resume study drug/regimen.

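### For durvalumab, Table 9 and Appendix 4 give different instructions for Grade 4 (and Grade 2) endocrine immune-related events, no text says which governs, and Appendix 4's reach over mocetinostat is unclear

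*Protocol*

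**What the plan says.** Section 5.2.8 assigns Table 9 and Appendix 4 to durvalumab, Table 9 as the general guide and Appendix 4 as the fuller guide by type of event.

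- **Table 9, Grade 4 row:** "permanently discontinue". The one note in that row is about pancreatic enzymes: "For Grade 3 and above asymptomatic amylase or lipase levels hold study drug/regimen".
- **Table 9, Grade 3 row:** "Depending on the individual toxicity, may permanently discontinue. Refer to guidelines below".
- **Table 9, Grade 2 row:** hold until Grade 1 or less, for any immune-related event. The same row adds "Patients with endocrinopathies who may require prolonged or continued steroid replacement can be retreated on the following conditions".
- **Appendix 4, Endocrinopathy, Grade 3 or 4 row:** "For Grade 3 or 4 endocrinopathy other than hypothyroidism, hold dose until endocrinopathy symptom(s) are controlled". It continues "Can be resume at the next scheduled dose once event stabilizes to grade" 1 or less, with 5 to 7 days elapsed since the end of the steroid taper.
- **Appendix 4, Endocrinopathy, Grade 2 row:** the hold applies to endocrinopathy except hypothyroidism.
- **Appendix 4, Endocrinopathy, both of those rows:** "Isolated hypothyroidism may be treated with replacement therapy without treatment interruption and without corticosteroids".

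For the other drug, Section 5.1.8.1 says "In the event of an irAE, administration of mocetinostat should be interrupted until the event stabilizes" to Grade 1 or less and any steroid taper is complete. It names endocrinopathies among the events it has in mind, sets no lower grade limit, and describes its rule as similar to the durvalumab resumption guidance in Table 9 and Appendix 4.

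**The concern.** A site with a patient who has a Grade 4 endocrinopathy finds two instructions for durvalumab. One ends the drug for good; the other pauses it and allows a return. Which one the patient gets depends on the page the site opens. Opposite stopping instructions are a patient-safety matter, and they also make time on durvalumab depend on the site for reasons unrelated to the patient. The Grade 2 mismatch does the same on a smaller scale for hypothyroidism. The mocetinostat question matters because sites must handle two drugs for one event, and the protocol does not say whether the detailed endocrine table speaks to both.

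**Working it through.** No sample size, error rate or event count bears on the inconsistency, so the check is a comparison of texts.

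**Step 1: durvalumab, text against text.**

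| Event | Table 9 | Appendix 4, Endocrinopathy |
|---|---|---|
| Grade 4, not hypothyroidism | Stop permanently | Hold, then may resume |
| Grade 4, isolated hypothyroidism | Stop permanently | May be treated without interruption |
| Grade 3 | Depends on the toxicity; refers on | Hold, then may resume (hypothyroidism excepted) |
| Grade 2, not hypothyroidism | Hold | Hold |
| Grade 2, isolated hypothyroidism | Hold | Outside the hold; may be treated without interruption |

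Grade 3 is consistent because Table 9 defers to the individual toxicity. Both Grade 4 lines and the Grade 2 hypothyroidism line are not.

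**Step 2: look for a rule that settles it.**
- The Grade 3 row of Table 9 refers the reader onward; the Grade 4 row does not.
- Table 9's conditions for retreating patients on steroid replacement stand in its Grade 2 row only.
- Table 9 lists its extra stopping conditions as additions to the severity criteria in Appendix 4. That points to Appendix 4 but does not say it overrides the Grade 4 row.
- Section 5.2.8 distinguishes general from detailed guidance without ranking them.
- Appendix 4 has eight event types. Seven stop permanently at Grade 4 (pneumonitis, diarrhea, hepatitis, nephritis, rash, neurotoxicity, neuromotor syndromes), in line with Table 9. Endocrinopathy alone departs, and nothing marks this as a deliberate exception.

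**Step 3: mocetinostat.** Section 5.1.8.1 is a mocetinostat rule. It and Section 5.2.8 both describe Table 9 and Appendix 4 as durvalumab guidance. On that reading the rules differ by drug and do not clash. But Appendix 4 speaks of treatment interruption in the hypothyroidism line and of study drug or study regimen elsewhere, and SAP Section 9.3 takes study treatment to mean either drug or both. On that reading they would clash. The documents do not choose between the two.

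**Step 4: how often Grade 4 could arise.** The documents give no Grade 4 endocrine rate. Section 1.3.3 lists treatment-related events of Grade 3 or above seen in at least 2 of 970 durvalumab monotherapy patients. No thyroid, pituitary or adrenal term is listed, so each occurred in at most 1. (Hyperglycaemia is listed, but the protocol keeps diabetes separate from endocrinopathy.)
- Maximum Phase 2 enrolment: 17 + 44 + 100 + 100 = 261.
- Per term: 1/970 = 0.10%, and 261 × 1/970 = 0.27 patients at most.
- If each of the four named endocrine events (hypophysitis, adrenal insufficiency, hyper- and hypothyroidism) had occurred once: 261 × 4/970 = 1.08 patients.

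Grade 4 is a subset of these.

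**The case against.** The best defence is that the specific text refines the general one. Table 9 points to Appendix 4 for severity-based discontinuation. The continuation of Table 9 already qualifies its Grade 4 rule outside the row, for inflammatory reactions attributed to local tumour response. Appendix 4 also softens Table 9's Grade 2 hold elsewhere, for rash and sensory neuropathy. For endocrinopathy other than hypothyroidism, both texts stop dosing at onset and part only over later resumption, and the Appendix 4 row tells the site to talk to the study physician. All of this is fair, and it makes a harmful outcome less likely. It does not remove the conflict: a reader must infer the precedence, and the contrast between Table 9's Grade 3 and Grade 4 rows invites the opposite inference.

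Three stronger readings are tempting, and the documents do not support them.

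- **That Section 5.1.8.1 contradicts Appendix 4 on hypothyroidism and on steroids.** The hypothyroidism wording is permissive and stands in guidance assigned to durvalumab. Finishing a taper is compatible with staying on replacement steroids: Table 9's Grade 2 row contains both. What remains is unclear scope.
- **That about 16 patients are affected.** Treatment-related hypothyroidism was 6.3% in Section 1.3.3, and 0.063 × 261 = 16.4. That rate covers all grades and is applied to maximum enrolment. It does not measure the Grade 4 conflict.
- **That the Grade 4 conflict disturbs DLT evaluability or the choice of RP2D.** Under Sections 3.1.1 and 3.1.2, a related Grade 4 immune event in Cycle 1 is a DLT, and a patient with a DLT is evaluable whatever the dose count. Under Section 3.1.4, a dose level with a related immune event of Grade 3 or above already fails the RP2D definition, so dose intensity does not decide the matter.

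**Conclusion.** The point holds as an internal inconsistency in the durvalumab guidance: a direct conflict at Grade 4 between Table 9 and Appendix 4, a lesser one at Grade 2 for hypothyroidism, and no statement of which text governs. Whether Appendix 4's endocrine allowances reach mocetinostat is an open question of scope and should be reported only as that.

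In numbers the Grade 4 conflict is small: well under one expected patient per endocrine term, and about one at most under the four-term bound, at full Phase 2 enrolment. That bound assumes the monotherapy rate carries over to the combination, which is untested; Section 1.4 itself warns that mocetinostat might exacerbate these events. The reason to act is the opposite stopping instructions, not their frequency. The ORR analysis and the sample sizes do not depend on this point, and nothing here says which clinical rule is right.

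**What to change.** Reconcile Section 5.1.8.1, Section 5.2.8, Table 9 and the endocrinopathy rows of Appendix 4:

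1. Give each grade of endocrine immune-related event one instruction per drug, with hypothyroidism addressed explicitly at Grades 2, 3 and 4.
2. State which text governs when Table 9 and Appendix 4 differ.
3. State whether Appendix 4 applies to mocetinostat, including the allowances for isolated hypothyroidism and for continued steroid replacement.

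The sponsor's medical team decides the clinical content. The cost is wording, issued by administrative letter or amendment with the IRB/EC submission that Section 13.1 requires. No assessment, sample size or analysis changes.

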#### Appendix 4 Management of Specific Immune-Related Adverse Events (Continued)

Immune mediated Neurotoxicity (to include but not limited to limbic encephalitis, autonomic neuropathy, excluding Myasthenia Gravis and Guillain-Barre)		

 
• Patients should be evaluated to rule out any alternative etiology (e.g., disease progression, infections, metabolic syndromes and medications, etc.)
 
• Monitor patient for general symptoms (headache, nausea, vertigo, behavior change, or weakness)
 
• Consider appropriate diagnostic testing (e.g. electromyogram and nerve conduction investigations)
 
• Symptomatic treatment with neurological consult as appropriate
 
		
Grade of AE	Dose Modifications	Toxicity Management
Grade 1	
 
• None required
 
	
 
• See recommendations above.
 

Grade 2	
 
• For acute motor neuropathies or neurotoxicity, hold dose until resolution to <math>\leq</math> Grade 1
 
• For sensory neuropathy/neuropathic pain, consider holding dose until resolution to <math>\leq</math> Grade 1.
 
• If toxicity worsens then treat as Grade 3 or Grade 4
 
• Can resume once event improves to Grade <math>\leq</math> 1 and after completion of steroid taper.
 
	
 
• Discuss with the study physician
 
• Obtain Neurology Consult
 
• Sensory neuropathy/neuropathic pain may be managed by appropriate medications (e.g., gabapentin, duloxetine, etc.)
 
• Promptly start systemic steroids prednisone 1-2mg/kg/day PO or IV equivalent
 
• If no improvement within 3-5 days despite 1-2mg/kg/day prednisone PO or IV equivalent consider additional workup and promptly treat with additional immunosuppressive therapy (e.g. IVIG)
 

Grade 3	
 
• Hold until resolution to <math>\leq</math> Grade 1
 
• Permanently discontinue if Grade 3 irAE does not resolve to <math>\leq</math> Grade 1 within 30 days.
 
	
 
• For Grade 3 or 4:
 
• Discuss with study physician
 
• Obtain Neurology Consult
 
• Consider hospitalization
 
• Promptly initiate empiric IV methylprednisolone 1-2 mg/kg/day or equivalent
 

Grade 4	
 
• Permanently discontinue
 
	
 
• If no improvement within 3-5 days despite IV corticosteroids, consider additional workup and promptly treat with additional immunosuppressants (e.g. IVIG)
 
• Once stable, gradually taper steroids over <math>\geq</math> 28 days
 

## Appendix 4 Management of Specific Immune-Related Adverse Events (Continued)

Immune-mediated peripheral neuromotor syndromes, such as Guillain-Barre and Myasthenia Gravis
 
 
Prompt diagnosis of immune-mediated peripheral neuromotor syndromes is important, since certain patients may unpredictably experience acute decompensations which can result in substantial morbidity or in the worst case, death. Special care should be taken for certain sentinel symptoms which may predict a more severe outcome, such as prominent dysphagia, rapidly progressive weakness, and signs of respiratory insufficiency or autonomic instability
 
Patients should be evaluated to rule out any alternative etiology (e.g., disease progression, infections, metabolic syndromes and medications, etc.). It should be noted that the diagnosis of immune-mediated peripheral neuromotor syndromes can be particularly challenging in patients with underlying cancer, due to the multiple potential confounding effects of cancer (and its treatments) throughout the neuraxis. Given the importance of prompt and accurate diagnosis, it is essential to have a low threshold to obtain a neurological consult
 
Neurophysiologic diagnostic testing (e.g., electromyogram and nerve conduction investigations, and “repetitive stimulation” if myasthenia is suspected) are routinely indicated upon suspicion of such conditions and may be best facilitated by means of a neurology consultation
 
Important to consider that the use of steroids as the primary treatment of Guillain-Barre is not typically considered effective. Patients requiring treatment should be started with IVIG and followed by plasmapheresis if not responsive to IVIG
 
		
Grade of AE	Dose Modifications	Toxicity Management
Grade 1	
 
None required
 
	
 
Discuss with the study physician
 
Care should be taken to monitor patients for sentinel symptoms of a potential decompensation as described above
 
Obtain a neurology consult unless the symptoms are very minor and stable
 

Grade 2	
 
Hold until <math>\leq</math> Grade 1
 
Permanently discontinue if does not resolve within 30 days or if there are signs of respiratory insufficiency or autonomic instability
 
	
 
Discuss with the study physician
 
Care should be taken to monitor patients for sentinel symptoms of a potential decompensation as described above
 
Obtain a Neurology Consult
 
Sensory neuropathy/neuropathic pain may be managed by appropriate medications (e.g., gabapentin, duloxetine, etc.)
 
MYASTHENIA GRAVIS
 
Steroids may be successfully used to treat Myasthenia Gravis. Important to consider that steroid therapy (especially with high doses) may result in transient worsening of myasthenia and should typically be administered in a monitored setting under supervision of a consulting neurologist.
 
Patients unable to tolerate steroids may be candidates for treatment with plasmapheresis or IVIG. Such decisions are best made in consultation with a neurologist, taking into account the unique needs of each patient.
 
If Myasthenia Gravis-like neurotoxicity present, consider starting acetylcholine esterase (AChE) inhibitor therapy in addition to steroids. Such therapy, if successful, can also serve to reinforce the diagnosis.
 
GUILLAIN-BARRE: Important to consider here that the use of steroids as the primary treatment of Guillain-Barre is not typically considered effective. Patients requiring treatment should be started with IVIG and followed by plasmapheresis if not responsive to IVIG.
 

